7.4.2 Discontinuations from Study Medication

Discontinuation from study medication is defined as subject's termination of the study medication (abatacept or placebo) without resumption prior to study completion. A subject will be considered as discontinued from study period if and only if the subject status CRF page indicates he/she did not complete that specific study period. The summary of discontinuations is provided in [Section 7.3.1](#).

7.4.3 Treatment Compliance

The number of subjects with missed infusions in the double-blind period (excluding missed infusions due to premature discontinuation from study) will be summarized by treatment group and number of missed infusions. An interruption of infusion on a particular day will not be counted as a 'missed' infusion. This summary will be performed with the ITT Analysis Population. A listing of all missed infusions indicating the period will be also provided.

[REDACTED]

7.5 Efficacy

The primary and secondary efficacy analyses (defined in [section 7.5.2](#) and [7.5.4](#)) will be performed using the ITT Analysis Population by treatment group assigned at randomization during the double-blind period. The primary analysis will be repeated using the PP analysis population if more than 10% of subjects in any treatment group meet the criteria for a relevant protocol deviation. All other efficacy analyses will be performed using the ITT Analysis Population, unless otherwise specified.

The efficacy analysis in this analysis plan is mainly focused on the double-blind period.

7.5.1 Analysis of Primary Efficacy Endpoint

The primary objective of the study is the comparison of renal response, defined by composite renal index, at Day 113 at the end of double-blind period between abatacept and placebo arms. The definition and computation method for renal response is provided in [Section 8.1.1](#).

The primary comparison of proportion of subjects in renal response at Day 113 at the end of double-blind period between abatacept and placebo arms will be assessed using a logistic regression model. The logistic regression model will adjust for baseline UPCR, baseline eGFR and the randomization stratification variables of Genotype (APOL1 high risk group vs. Others) and Age (< 18 y vs. ≥ 18 y). Point estimate of the adjusted Odds Ratios (OR) of the odds of achieving renal response in the abatacept arm compared to the placebo arm, corresponding 95% CI and p-value, will be provided. Unadjusted point estimate of the proportion of renal response in each treatment arm and corresponding 95% CI will also be provided. All subjects who discontinue prematurely prior to reaching the primary endpoint, and subjects with missing data for response at Day 113 assessment visit, will be considered as not achieving response in the primary analysis. The primary analysis will be based on the ITT Analysis Population.

7.5.2 Sensitivity Analysis

Since the balance intended in the stratification by Genotype (APOL1 high risk group vs. Others) may be impacted by the number of subjects who choose to refuse genotyping and consequently considered in the “Others” Genotype group, sensitivity analysis of the primary endpoint will be performed. The sensitivity analysis will use a logistic regression model that does not adjust for the stratification factor of Genotype based on the ITT Analysis Population. The comparison between the proportion of subjects in renal response at Day 113 at the end of double-blind period in abatacept and placebo arm will be assessed using a logistic regression model adjusting only for Age (< 18 y vs. ≥ 18 y), baseline UPCR and baseline eGFR. Point estimate of the adjusted Odds Ratios (OR) of the odds of achieving renal response in the abatacept arm compared to the placebo arm, corresponding 95% will be provided. As in the primary analysis, all subjects who discontinue prematurely prior to reaching the primary endpoint, Day 113 assessment visit and subjects with missing data for response at Day 113 assessment visit, will be considered as not achieving response in the primary analysis.

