2.2 Treatment Assignment

Subjects are randomized in a 1:1 ratio within each of the strata to the abatacept or placebo treatment arms across all sites in the double-blind period. The randomization will be stratified by Genotype for whom test results, obtained either prior to enrollment or at screening, are available (APOL1 high risk group vs. Others) and Age (< 18 y and \geq 18 y). Subjects who refuse genotyping will be considered as in the “Others” Genotype group.

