5 SAMPLE SIZE AND POWER

This pilot study is planned to randomize approximately 90 subjects to assess the primary endpoint of proportion subjects in Renal Response at Day 113 between the abatacept and placebo arms. The randomization will be stratified by Genotype for whom test results, obtained either prior to enrollment or at screening, are available (APOL1 high risk group vs. Others) and Age (< 18 y and ≥ 18 y).

A total of 90 subjects randomized in a 1:1 ratio to abatacept vs. placebo will yield approximately 80% power to detect a treatment difference (delta) of 28% between the two treatment arms. This power estimate assumes a 2-sided alpha level of 5%, and Renal Response rate of 40% and 12% in the abatacept and placebo arms respectively. The 12% estimate of Renal Response in the placebo arm was based on observed rate of Renal Response in the FONT II study³ which has a similar population that is proposed for the present study and expert opinion.

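### The SAP's check on genotyping refusals never uses refusal status, so its agreement or disagreement with the primary result says essentially nothing about refusals

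*SAP*

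**What the plan says.** SAP 2.2 stratifies randomization by genotype (APOL1 high risk vs. Others) and age, and states that "Subjects who refuse genotyping will be considered as in the" Others group. SAP 7 takes genotype for the models from IxRS.

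SAP 7.5.1 defines the primary model: "The logistic regression model will adjust for baseline UPCR, baseline eGFR and the randomization stratification variables of Genotype" and age, in the ITT population, with missing or discontinued subjects counted as non-responders.

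SAP 7.5.2 argues that the intended genotype balance "may be impacted by the number of subjects who choose to refuse genotyping". It then plans one analysis, in the ITT population: "The sensitivity analysis will use a logistic regression model that does not adjust for the stratification factor of Genotype". Age, baseline UPCR, baseline eGFR and the non-responder rule are unchanged. It asks for an odds ratio and 95% interval, with no p-value.

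Protocol 8.4.2.1 describes a different sensitivity model, which drops both stratification factors and gives no refusal rationale. It does not use refusal status either. Refusers are eligible (Protocol 3.3.1), and no expected refusal rate is given.

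**The concern.** The stated worry and the planned remedy do not meet. Because refusers are randomized inside Others, the arms are balanced on the coded stratum by design. Two things remain unknown about refusers: their true genotype, and whether they respond differently. Deleting the genotype term addresses neither, and it also removes the adjustment for every subject who was genotyped.

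This is the only analysis labelled a sensitivity analysis of the primary endpoint in the readable SAP. If the two odds ratios agree, the report could present the result as robust to refusals when refusals were never tested. If they differ, refusals could be blamed for a shift that comes from dropping a prognostic covariate.

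**Working it through.** **Inputs from the documents.** 90 subjects, 45 per arm; "Renal Response rate of 40% and 12% in the abatacept and placebo arms respectively"; two-sided alpha 5% (SAP 5). Model terms are from SAP 7.5.1 and 7.5.2.

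**Assumed, not in the documents.** High-risk prevalence 20-40%; odds ratio for response, high risk vs. other, 0.1 to 1.0; refusal 0-80%; blocks of 4; 40% in one age stratum.

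**1. The plan's own figure.** With mean rate 0.26, the uncorrected size per arm is (1.96·√(2·0.26·0.74) + 0.8416·√(0.40·0.60 + 0.12·0.88))² / 0.28² = 37.3. The continuity correction gives (37.3/4)·(1 + √(1 + 4/(37.3·0.28)))² = 44.2, so 45 per arm. Continuity-corrected power at 45 per arm is 80.9%, so the stated 80% is reproduced.

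**2. Limiting cases, with no assumptions.** If everybody refused, all subjects would be coded Others. The genotype term would be constant, the two SAP models would be identical, and the gap would be exactly zero when miscoding is at its worst. If nobody refuses, the models still differ by a real covariate. A three-level term behaves as such a check should: with no refusals it reduces to the primary model.

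**3. Large-sample gap.** Take 40% high-risk and genotype odds ratio 0.2. Response rates that reproduce the SAP's margins are:

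| | High risk | Other | Overall |
|---|---|---|---|
| Placebo | 0.0402 | 0.1732 | 0.4·0.0402 + 0.6·0.1732 = 0.12 |
| Abatacept | 0.1901 | 0.5399 | 0.4·0.1901 + 0.6·0.5399 = 0.40 |

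The treatment odds ratio is (0.1901/0.8099)/(0.0402/0.9598) = 5.60 in high risk and (0.5399/0.4601)/(0.1732/0.8268) = 5.60 in the rest. Without genotype it is (0.40/0.60)/(0.12/0.88) = 4.89. The ratio is 4.89/5.60 = 0.87 with no refusals and no confounding; this is non-collapsibility alone. At genotype odds ratio 0.5 the ratio is 0.97. With refusals (odds ratio 0.2) it moves toward 1: 0.91, 0.94 and 0.98 at 20, 40 and 80% refusal.

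**4. Simulated trials of 90** (about 2,400 to 3,000 usable replicates per scenario in the main set). A gap above 10% means |difference in log odds ratio| > ln 1.10.

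With no refusals and 30% high-risk:

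| Genotype odds ratio | Trials with gap above 10% |
|---|---|
| 1.0 (not prognostic) | 3-6% |
| 0.5 | 16% |
| 0.33 | 29% |
| 0.25 | about 43% |
| 0.1 | 78% |

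The 3%, 29% and 78% runs omitted UPCR and eGFR, and the 6%, 16% and 43% come from a separate set, so the series is approximate.

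With refusals, the SAP gap was compared with the shift that true genotypes would cause. The correlation was -0.05 to +0.03 when genotype is prognostic. At genotype odds ratio 0.33, when true genotypes moved the odds ratio by more than 10%, the SAP gap stayed under 10% in 40, 60 and 78% of trials at 10, 20 and 40% refusal.

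**5. Analyses that use refusal status** (30% high-risk, genotype odds ratio 0.33). Median treatment odds ratios:

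| Scenario | Primary | SAP 7.5.2 | Three-level | Genotyped only |
|---|---|---|---|---|
| 40% refuse, same effect in refusers | 5.27 | 5.00 | 5.38 | 5.64 |
| 20% refuse, no effect in refusers | 4.21 | 4.05 | 4.54 | 5.60 |
| 40% refuse, no effect in refusers | 3.10 | 3.03 | 3.33 | 5.75 |

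A separate set of runs gave 3.21 (primary), 3.18 (SAP 7.5.2) and 6.12 (genotyped only) for the last scenario. Only the genotyped-only fit clearly shows the refusers' influence.

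**The case against.** The strongest reply is that SAP 7.5.2 sets no threshold and no rule for reading a gap, so the misreading is hypothetical. It may only ask whether the result depends on a covariate that could be misclassified, and omitting the covariate answers that. This stands for the modest question, but the section names refusals as its reason, and on refusals the answer is empty.

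The gap is also small against sampling error. At the planned rates the standard error of the unadjusted log odds ratio is √(1/18 + 1/27 + 1/5.4 + 1/39.6) = 0.55, so the 95% interval spans a factor of exp(1.96·0.55) = 2.9 each way. The mean gap with no refusals, at genotype odds ratio 0.25, is 0.111, or 0.111/0.55 = 0.20 of a standard error. This stands, and it is why the point concerns interpretation.

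The alarming frequencies need a strong genotype effect, which the documents do not quantify. This stands too.

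A three-level term is no cure. It gives all refusers one intercept, and its correlation with the true-genotype shift is only about 0.2-0.3. That is why it should not be the only replacement.

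Other analyses exist: unadjusted proportions, APOL1 subgroups and a conditional per-protocol repeat. None tests refusals, and SAP 7.5.5 does not say whether refusers count as undetermined for APOL1.

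**Conclusion.** The point holds as a fault in what the check can show. SAP 7.5.2 cannot inform on the concern it names: the gap can appear without refusals, shrinks as they rise, and is uncorrelated with their effect when genotype is prognostic.

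Three stronger readings are tempting and are not supported:

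- A reader might infer that refusals bias the primary test. They do not, because refusers are randomized 1:1 within Others.
- A reader might infer that the trial's conclusion is at risk. Significance differed between the two models in only about 0.5-2.8% of simulated trials, and no p-value is planned for this analysis.
- A reader might infer that the gap carries no information of any kind. Its average size does depend weakly on the refusal rate, though in the wrong direction. If genotype is not prognostic, its correlation with the miscoding shift is 0.26-0.42, but large gaps are then rare.

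The size of the false-alarm risk depends on prevalence and genotype effect, both assumed here, and is negligible if genotype is not prognostic. That this is the only sensitivity analysis can be said of the readable text only.

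**What to change.** In SAP 7.5.2, prespecify two analyses that use refusal status:

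- (a) The primary model in genotyped subjects only. Genotyping status is fixed before randomization, so the comparison remains a randomized one.
- (b) The primary model in the full ITT population with genotype at three levels: high risk; genotyped, not high risk; not genotyped. Fit it only if the not-genotyped group reaches a minimum size set before unblinding.

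The genotype-dropped model may stay as supplementary, without the claim that it addresses refusals. Reconcile SAP 7.5.2 with Protocol 8.4.2.1 in the same edit.

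**Costs.**

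- One SAP paragraph.
- Analysis (a) loses precision. At 40% refusal 54 subjects remain, and the standard error grows to about 0.55·√(90/54) = 0.71. It will differ from the primary odds ratio by chance, so report it with its interval and without a percentage-change threshold.
- Analysis (b) adds one parameter with 45·0.40 + 45·0.12 = 23.4 expected responders, or 23.4/6 = 3.9 per term against 23.4/5 = 4.7 in the primary model. It only partly tracks the effect of unknown genotype.
- The minimum size matters. With 9 refusers split evenly, the chance that none responds is (0.60·0.88)^4.5 = 0.06; with 4.5 on average it is (0.60·0.88)^2.25 = 0.24.
- Not-genotyped status must be identifiable from screening data, because the IxRS stratum alone does not separate it.

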7.5.3 Analysis of Secondary Efficacy Endpoints

- Mean change from baseline in UPCR at Day 113: Longitudinal (repeated measure) mixed model will be used to assess this endpoint. The model will include treatment group, UPCR baseline value and randomization stratification factors (genotype and age), time, baseline value by time interaction, time by treatment interaction as fixed effects and subject as a random effect. An unstructured covariance matrix will be used to model the correlation of the repeated measures within each subject. The SAS procedure PROC MIXED will be used with the restricted maximum likelihood (REML) method for estimation and the denominator degrees of freedom will be calculated according to the Kenward Roger method. Adjusted mean change

from baseline by treatment groups and associated standard errors (SE) will be presented as well as treatment differences versus placebo with 95% confidence intervals. A summary will be provided, presenting the mean change from baseline in UPCR at each time point in double-blind period as described above. In addition:

- Summary of mean change from baseline in UPCR at each time point during double-blind period and OLE will be provided. This summary will be descriptive without adjusting for stratification or baseline factors.
- Graphs of median percent change from baseline in UPCR during all periods will be presented.
- Protein excretion determinations from 24 hour urine collections are considered to be more reliable than those obtained from spot urine collections. This is due primarily to the variability in the protein loss over the course of the day in chronic kidney diseases (CKD). This variability may not be similar between different forms of CKD. To help determine the degree of variability that may exist in subjects with TRNS (FSGS/MCD), UPCR are to be taken from a 24-hour urine collection on Day 1 and 113; if not possible, then from a single voided specimen. To assess the relationship between the two measurements a correlation analysis will be performed between the two measurements as an exploratory analysis. The analysis will be performed if more than 50% of subjects have both 24-hour collection and single voided specimen paired. The correlation between the 24-hour UPCR and single-void UPCR will be examined using the Pearson correlation coefficient or Kendall's Tau if either measure is not normally distributed; the estimate of the correlation coefficient and corresponding 95% CI will be provided; all subjects will be combined into one group for this analysis.
- Mean change from baseline in serum albumin at Day 113. A similar mixed model used in the above secondary endpoint will be applied for this endpoint. Adjusted mean change from baseline by treatment group and associated standard errors (SE) will be presented as well as treatment differences versus placebo with 95% confidence intervals will be provided. A summary will be provided, presenting the mean change from baseline in serum albumin at each time point in double-blind period as described above.
 - Additional summary of mean change from baseline in serum albumin at each time point during OLE will be provided. This summary will be descriptive without adjusting to stratification or baseline factors and will be presented by treatment arm.
- The proportion of subjects achieving complete remission (defined in [Section 8.1.2](#): UPCR ≤ 0.3 with eGFR normal or $\geq 75\%$ baseline if below normal at baseline) at Day 113: the comparison in proportion of subjects achieving complete remission between the abatacept and placebo arms will be assessed using a logistic regression model. To account for randomization stratification, the logistic regression model will adjust for the randomization stratification variables of genotype and age in addition to adjusting for baseline UPCR and baseline eGFR. Point estimate of the adjusted Odds Ratios (OR) of the odds of achieving complete remission in the IV abatacept arm compared to the placebo arm, corresponding 95% CI, will be provided.
- Mean change from baseline in PROMIS measures at Day 113. Descriptive summary statistics for changes in patient reported outcomes of physical function, fatigue and pain improvement from baseline over time during double-blind period for the PROMIS static short forms will be provided by age group.

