- Double-blind period analysis: This analysis will be performed for the double-blind period when all subjects complete their Day 113 visit assessment or discontinue prematurely prior to Day 113. At the time of the first analysis the data will be unblinded. This analysis will include primary endpoint and secondary endpoints.
- End of study analysis: A second analysis will be performed at the end of the study when all subjects complete their open label extension (OLE) and follow-up period or discontinue prematurely.

This statistical analysis plan will describe the analysis to be performed at the end of the double-blind period and at the end of the study.

Prior to Protocol Amendment 2, the study design had a blinded-study drug period that was twice as long as the current double-blind period and was divided into 2 periods of equal length, known as Period 1 and Period 2, so that randomized subjects could switch blinded therapy. The current design eliminates Period 2 and renames the previous Period 1 as the double-blind period.

This modification does not impact the primary nor secondary study objectives. It does impact the exploratory objectives which addressed persistence of response and onset of response during Period 2, these are now eliminated.

For subjects who completed Period 1 and entered Period 2 prior to the protocol revision, the Period 1 data will be analyzed as part of the double-blind period since study execution during this timeframe is unchanged, the Period 2 data will only be listed. Period 2 data won't be part of any summaries except for safety summaries at the end of the study on the cumulative abatacept safety period.

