2 STUDY DESCRIPTION

2.1 Study Design

This is a phase II randomized, placebo-controlled, double-blind, parallel arm design study to evaluate the efficacy and safety of intravenous abatacept in treatment resistant nephrotic syndrome (Focal Segmental Glomerulosclerosis / Minimal Change) in adult and pediatric subjects.

This pilot study will randomize approximately 90 subjects 1:1 to intravenous (IV) abatacept or placebo in a double-blind (DB) fashion. The randomization will be stratified by Genotype for whom test results, obtained either prior to enrollment or at screening, are available (APOL1 high risk group vs. Others) and Age (< 18 y and ≥ 18 y).

The trial will consist of 4 periods: the screening period will be 28 days (can be extended an additional 14 days to complete testing by repeating screening labs), a 16 week double-blind treatment period (parallel arms: IV abatacept vs. IV placebo), a 168 day abatacept open label extension period (OLE), and a 6 month follow-up period.

Subjects randomized to abatacept treatment in the double-blind period will be dosed as follows. Adults will use the weight-tiered dose: < 60kg: 500mg, 60 to 100kg: 750mg, > 100kg: 1000mg;

pediatric patients 6 to 17 years who weigh < 75kg will receive:10mg/kg and those who weigh \geq 75kg will follow adult dosing. Dosing is on Day 1, 15, 29, 57, 85. Subject in the placebo arm will receive normal Saline or D5W following the same dosing schedule. In the OLE, subjects who enter will all receive age and weight-based IV abatacept every 28 days for 169 days.

The primary efficacy assessment, renal response (defined in [Section 8.1.1](#)), will be on Day 113. On Day 113, all subjects who choose to receive open label therapy with abatacept will enter the OLE. During the OLE, the durability (i.e., continuity of response) and stability (i.e., the change in urine protein/creatinine ratio (UPCR)) of response will be determined by continuing to capture and describe the same study outcomes among responders. Adjustment of background therapy will also be allowed during the OLE at the discretion of the investigators and subjects to determine the relative contribution (or need) of these agents for renal responses.

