6 STUDY PERIODS, TREATMENT REGIMENS AND POPULATIONS FOR ANALYSES

6.1 Study Periods

In this study, there are four study periods: screening period, double-blind period (DB), open label extension period (OLE), and follow-up period.

The following analysis periods defined below are for analysis purposes. The definitions below indicate the data to be included in the analysis of each specified period. Subjects discontinued during a specified period (DB or OLE) will be considered on-treatment for 56 and 42 days after the last dosing in that period for safety and efficacy analysis respectively. Follow-up period data will be included in one of the analysis periods depending on the time of completing the study.

Screening Period: Starts with the day of enrolment and ends prior or on the day of first dose of study medication (abatacept or placebo).

Double-Blind Period: Starts with the first dosing of double-blind study medication and ends 56/42 days (for safety/efficacy analysis) after the last dose of the double-blind period or the first dosing of OLE, whichever is earlier.

For subjects who completed Period 1 and entered Period 2 prior to Protocol Amendment 2, includes data from first dose date in Period 1 up to the first dose in Period 2.

Open Label Extension Period (OLE): Starts with the first dosing in the OLE and ends 56/42 (for safety/efficacy analysis) days after the last dose in the OLE.

Cumulative Abatacept Safety Period: Starts at the time of the first dose of abatacept (either in the double-blind period for the subjects randomized to abatacept or in the OLE for the subjects randomized to placebo) and continues up to 56 days post last dose of abatacept for safety (AE and laboratory summaries). The last abatacept dose can be last dose in double-blind period for subjects not treated in the OLE.

For subjects who completed Period 1 and entered Period 2 prior to the protocol revision:

- For subjects on abatacept during Period 1:
 - For subjects who do not enter OLE period: starts with the first dosing of Period 1 and ends 56 days after the last dosing of Period 1.
 - For subjects who enter OLE period: starts with the first dosing of Period 1 and ends 56 days after the last dosing of Period 1 combined with OLE period that starts with the first dosing in the OLE period and ends 56 days after the last dosing in the OLE period.
- For subjects on placebo during Period 1:

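### The open-label UPCR and albumin rows for the randomized abatacept arm include earlier-design subjects who spent Period 2 on placebo, so the later rows do not describe continued abatacept

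*SAP*

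**What the plan says.** **The earlier design.** SAP Schedule of Analyses explains that before Amendment 2 the blinded phase was "divided into 2 periods of equal length, known as Period 1 and Period 2, so that randomized subjects could switch blinded therapy". For subjects who had already entered Period 2, "the Period 2 data will only be listed", and those data are not to "be part of any summaries except for safety summaries at the end of the study on the cumulative abatacept safety period". This restriction covers Period 2 data only. Tables 8.6-2 and 8.6-4 give the same subjects their own OLE visit windows.

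**The OLE summaries.** For UPCR, SAP 7.5.3 says: "Summary of mean change from baseline in UPCR at each time point during double-blind period and OLE will be provided". For albumin it adds an OLE summary and says: "This summary will be descriptive without adjusting to stratification or baseline factors and will be presented by treatment arm". SAP Section 9 lists changes in UPCR and albumin as the efficacy content of the end-of-study report.

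**Grouping.** The UPCR sentence names no grouping. SAP 7.5 assigns the remaining efficacy analyses to the ITT population unless stated otherwise, and SAP 6.3.1 groups that population as randomized.

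**Time axis.** SAP 8.6 assigns visits by days since the first infusion of the study, not by OLE day.

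**The concern.** For legacy subjects the randomized arm no longer describes the treatment received by the time of the OLE. A subject labelled abatacept has had a full blinded period of placebo and then restarts. If a response was lost on placebo, the table would show that as a weaker effect in the abatacept row. The OLE is the part of the study meant to show whether response lasts and stays stable (SAP 2.1), so its later abatacept rows are likely to be read as durability evidence.

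The SAP deals with the switch for safety: SAP 6.1 and 7.4.1 have separate rules for each legacy sequence. The visible text has no matching rule for OLE efficacy.

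**Working it through.** The plan gives no figure for this point, so the check is day arithmetic on its schedule.

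**1. Direction of the switch (SAP 6.1).** For legacy subjects on abatacept in Period 1 who enter the OLE, the cumulative abatacept period "ends 56 days after the last dosing of Period 1 combined with OLE period that starts with the first dosing in the OLE period". Period 2 beyond those 56 days is left out. For legacy subjects on placebo in Period 1, it starts at the first Period 2 dose. The two sequences are therefore abatacept then placebo, and placebo then abatacept.

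**2. Key days.**
- Last scheduled Period 1 dose: Day 85 (SAP 2.1).
- Start of the OLE under the current design: Day 113 (Protocol 3.1.3).
- Start of the OLE for legacy subjects: Day 225 (Table 8.6-2). This agrees with two equal periods: 113 + 112 = 225.

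**3. Gap between active doses, abatacept-first legacy subjects.** 225 − 85 = 140 days = 20 weeks. The protocol's contraception rule (70 days = 5 half-lives) and SAP 7.4.1 (56 days, about 4 half-lives) both give 14 days per half-life, so 140 / 14 = 10 half-lives.

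**4. Abatacept row for UPCR, by study-day label.** Current subjects: weeks since first dose = (day − 1) / 7. Legacy subjects: weeks since restart = (day − 225) / 7.

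| Label | Current design, continuous abatacept | Legacy, restarted abatacept |
|---|---|---|
| Days 141, 169, 197, 225 | 20, 24, 28, 32 weeks | none (Period 2, listed only) |
| Day 253 | 36 weeks | 4 weeks |
| Day 281 | 40 weeks | 8 weeks |
| Days 309, 337, 365, 393 | none | 12, 16, 20, 24 weeks |

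The row is mixed at two labels and entirely legacy at the last four.

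**5. Albumin (chemistry windows).** Current OLE labels are Days 169, 225 and 281 (Table 8.6-3). Legacy OLE labels are Days 281, 337 and 393 (Table 8.6-4). Day 281 is mixed; Days 337 and 393 are legacy only.

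**6. Placebo row.** Current placebo completers start abatacept at about Day 113, at OLE entry. Legacy placebo-first subjects also start at about Day 113, at the first Period 2 dose. At Day 253 both are (253 − 113) / 7 = 20 weeks from first abatacept, and at Day 281 both are 24 weeks. On study-day labels they match.

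**7. If rows were aligned on OLE day instead.** At OLE Day 29, current placebo subjects are 28 / 7 = 4 weeks from first abatacept, and legacy placebo-first subjects are (112 + 28) / 7 = 20 weeks. The placebo row would then be mismatched. The abatacept row is mixed on either axis.

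**8. Size at the mixed labels.** If a share f of the row is legacy and legacy subjects differ from current ones by D UPCR units, the row mean shifts by f × D. Neither value is in the documents. Over an assumed f of 5% to 40% and D of 0.5 to 2, the shift runs from 0.05 × 0.5 = 0.025 to 0.40 × 2 = 0.8 units. At the legacy-only labels f is 100%.

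**9. A related conflict.** SAP 7.5.3 plans UPCR graphs over all periods, while Schedule of Analyses keeps Period 2 out of every non-safety summary.

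**The case against.** The strongest case against is that little depends on these tables. They are descriptive and not restricted to responders, although SAP 2.1 frames durability among responders. SAP 7.5 says the efficacy analysis centres on the double-blind period, and SAP Section 9 describes the closing report as mainly safety. Legacy subjects have their own window tables, so the sponsor may intend to show them apart. SAP 7.5 refers to a Section 7.5.4 that is not visible, and other text is redacted, so a rule may exist there. All of this stands as a limit on importance and certainty. It does not supply a rule: separate windows are not separate columns, and the visible text puts these subjects under the randomized arm (expressly for albumin, through the ITT rule for UPCR).

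Three stronger readings are tempting but unsupported.

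- *The placebo row is distorted too.* Not on the SAP's study-day labels (step 6). It would be only if rows were aligned on OLE day.
- *The abatacept mean at OLE entry is diluted in proportion to the legacy share.* No row shows this. Current subjects enter at Day 113, when legacy abatacept subjects are only finishing Period 1. Legacy entry at Day 225 falls in the Period 2 block, which is only listed.
- *Legacy abatacept subjects were without drug effect for 20 weeks.* The 140 days are the interval between active doses. SAP 6.1 treats subjects who discontinue as on treatment for 42 days (efficacy) or 56 days (safety) after the last dose. By analogy the gap would be 140 − 42 = 98 days or 140 − 56 = 84 days. These subjects are also back on abatacept in the rows at issue.

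**Conclusion.** The point holds for the abatacept row of the OLE summaries of UPCR and albumin. Followed as written, the plan mixes continuous and restarted abatacept at UPCR Days 253 and 281 and albumin Day 281. It leaves UPCR Days 309 to 393 and albumin Days 337 and 393 made up of legacy subjects alone. Those rows do not describe continued abatacept.

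The size cannot be stated, because the number of legacy subjects and their course on placebo are not given. If response persisted through Period 2, the mixed rows might barely move; if it was lost, they would understate the effect of continued treatment. The Day 113 primary and secondary comparisons are untouched, because Period 1 is analysed as the double-blind period. This is a minor correction to descriptive output. It rests on the scheduled days, on the ITT grouping applying to the UPCR summary, and on no contrary rule in the text that is not visible.

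**What to change.** In SAP 7.5.3 and Section 9:

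- Limit by-arm OLE efficacy summaries and graphs to subjects who entered the OLE directly from the double-blind period.
- List the legacy subjects' OLE efficacy data, as is done for Period 2, or show the two legacy sequences as separate columns.
- State whether OLE rows use study day or OLE day. Under OLE-day alignment the split is needed for the placebo row as well.
- Reconcile the all-periods UPCR graphs with the rule that Period 2 data are only listed.

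Table 9-2 needs no change for this point, since it covers safety and the cumulative abatacept period already handles the switch. The cost is some SAP wording, one grouping variable and slightly smaller numbers in the OLE rows. No further data need to be collected.
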